6.7.2 Vital signs

Vital signs will be summarised and listed.

For the summary tables of vital signs by visit, the last pre-dose vital sign assessment will be presented. If no dosing occurs at a visit, the last assessment recorded at the visit will be presented.

For the first 3 IMP dosing visits, subjects will be monitored after IMP administration for immediate drug reactions for a minimum of 30 minutes with vital signs taken at every 30 minutes or until stable, whichever is later. These measurements will be listed.

Potentially clinically significant values will be defined as displayed in [Table 2](#).

Table 2: Potentially clinically significant vital signs values

Protocol parameter	SI unit	PCS low	PCS high
Systolic blood pressure	mmHg	<90 and decrease from baseline ≥ 20	≥ 180 and increase from baseline ≥ 20
Diastolic blood pressure	mmHg	<50 and decrease from baseline ≥ 15	≥ 105 and increase from baseline ≥ 15
Pulse	beats/min	<50 and decrease from baseline ≥ 15	≥ 120 and increase from baseline ≥ 15

Trial ID: LP0162-1343	Date: 15-Jun-2021	Version: 1.0 Page 16 of 22
-----------------------	-------------------	-------------------------------

Abbreviations: PCS=potentially clinically significant.

6.7.3 Electrocardiogram

Electrocardiogram (ECG) data will be summarised and listed. The overall central evaluation of ECG will be presented using shift tables.

6.7.4 Laboratory data

Laboratory data will be summarised and listed.

For the laboratory values, if the value is below the lower limit of quantification, half of the lower limit will be used for quantitative summaries. If the value is above the upper limit of quantification, the upper limit value will be used.

If more than one laboratory value is reported for the same visit and time point, the latest value will be used in summary statistics and analyses.

Shift tables from baseline to highest/lowest post-baseline value in the treatment period will be based on laboratory ranges. The laboratory ranges are defined for fasting values.

Shift tables for eosinophil values from baseline to end of treatment period and to highest/lowest post-baseline value in the treatment period will be summarised in the following categories: $\leq 0.5 \cdot 10^9/L$, $> 0.5 \cdot 10^9/L$ to $\leq 1.5 \cdot 10^9/L$, and $> 1.5 \cdot 10^9/L$.

Potentially clinically significant values will be defined as displayed in [Table 3](#).

Trial ID: LP0162-1343	Date: 15-Jun-2021	Version: 1.0 Page 17 of 22
-----------------------	-------------------	-------------------------------

Table 3: Potentially clinically significant biochemistry and haematology values

Protocol lab parameter	SI unit	PCS low	PCS high
Biochemistry			
Sodium	mmol/L	< 129 mmol/L, < 125 mmol/L	> 160 mmol/L
Potassium	mmol/L	< 3 mmol/L, < 2.5 mmol/L	> 6.5 mmol/L, > 7.5 mmol/L
Creatinine	umol/L	N/A	> 1.5xULN, > 3xULN
Calcium	mmol/L	< 1.9 mmol/L	> 3.0 mmol/L, > 3.5 mmol/L
Alkaline phosphatase	U/L	N/A	> 3xULN
Aspartate aminotransferase	U/L	N/A	> 3xULN, > 5xULN, > 10xULN, > 20xULN
Alanine aminotransferase	U/L	N/A	> 3xULN, > 5xULN, > 10xULN, > 20xULN
Bilirubin	umol/L	N/A	> 2xULN
Cholesterol	mmol/L	N/A	> 6.2 mmol/L
LDL cholesterol	mmol/L	N/A	> 4.1 mmol/L, > 4.9 mmol/L
HDL cholesterol	mmol/L	N/A	> 1.6 mmol/L
Triglycerides	mmol/L	N/A	> 2.3 mmol/L, > 5.6 mmol/L
Glucose (non-fasting)	mmol/L	< 3.9 mmol/L	> 11.1 mmol/L
Haematology			
Haemoglobin	g/L	< 110 g/L, < 80 g/L	> 185 g/L for male, > 165 g/L for female
Neutrophils, absolute count	$10^9/L$	< $1.5 \times 10^9/L$, < $1.0 \times 10^9/L$, < $0.5 \times 10^9/L$	N/A
Lymphocytes, absolute count	$10^9/L$	< $1.0 \times 10^9/L$, < $0.5 \times 10^9/L$	> $5.0 \times 10^9/L$
Monocytes, absolute count	$10^9/L$	< $0.1 \times 10^9/L$	> $0.8 \times 10^9/L$
Eosinophils, absolute count	$10^9/L$	N/A	> 1.5, > 5.0
Basophils, absolute count	$10^9/L$	N/A	> 0.2
Thrombocytes	$10^9/L$	< $100 \times 10^9/L$, < $30 \times 10^9/L$, < $10 \times 10^9/L$	> $450 \times 10^9/L$

Abbreviations: HDL = high density lipoprotein; LDL = low density lipoprotein; N/A = not applicable; PCS = potentially clinically significant; ULN = upper limit of normal (i.e., upper limit of normal reference range).

Trial ID: LP0162-1343	Date: 15-Jun-2021	Version: 1.0 Page 18 of 22
-----------------------	-------------------	-------------------------------

6.7.5 Urinalysis

Urinalysis data will be summarised and listed.

6.7.6 Pharmacokinetics and anti-drug antibodies

Pharmacokinetics and anti-drug antibodies (ADA) data will be summarised and listed.

6.8 General Principles

In addition to what is stated in the protocol, the lower and upper quartiles will be used to summarise continuous data.

6.8.1 Baseline value

Unless otherwise specified, the baseline value is defined as the latest pre-dose assessment.

Missing baseline assessments

When the baseline value is missing, endpoints concerning a change from baseline cannot be derived, and such subjects will be excluded from the analysis. Since the missingness of baseline values are unrelated to the assigned treatment, bias should not be a concern with this approach.

6.8.2 Definition of trial periods and date of permanent discontinuation of IMP

Date of permanent discontinuation of IMP

Defined for subjects who have a reason for permanent discontinuation of IMP recorded.

Defined as the latest of date of early termination visit (if existing) or date of onset of latest AE leading to withdrawal of trial product, otherwise date of the last visit, excluding safety follow-up and nominal Week 16 visits.

Exposure start

Date and time of first dose.

Exposure end

Date of Week 16 visit (if existing) at time 23:59:00, otherwise date of permanent discontinuation of IMP (if existing) at time 23:59:00, otherwise date of last IMP administration at time 23:59:00.

Trial ID: LP0162-1343	Date: 15-Jun-2021	Version: 1.0 Page 19 of 22
-----------------------	-------------------	-------------------------------

Date of last contact

Date of very last contact found by examining all time and date information in eCRF, laboratory, ECG, and PRO.

Trial periods

The time from exposure start to exposure end will be assigned to the treatment period and remaining time after exposure end will be assigned to the safety follow-up period as shown in [Table 4](#) (ADaM variable APHASE). The ADaM variable APERIODC will indicate the latest treatment at any given time point, thus not including a follow-up period ([Table 5](#)).

Table 4: Start and end time of trial periods (ADaM variable APHASE)

APHASE	Start of period	End of period (only if start date exists)
Treatment period	Exposure start	Exposure end
Safety follow-up period ¹	First day after exposure end	Date of last contact at time 23:59:00

1) Only applicable if date of last contact is not equal to date of exposure end.

Table 5: Start and end time of trial periods (ADaM variable APERIODC)

APERIODC	Start of period	End of period (only if start date exists)
Treatment period	Exposure start	Date of last contact at time 23:59:00

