10.2.2 Reasons for temporary discontinuation of IMP

IMP administration may be temporarily suspended in the event of:

- Other intercurrent illnesses or major surgery.
- An infection that requires parental treatment with antibiotic, antifungal, antiviral, anti-parasitic, or anti-protozoal agents.

IMP administration should be temporarily suspended in the event of:

- Treatment with systemic corticosteroids or non-steroidal immunosuppressive/immunomodulating medications (e.g. cyclosporine, methotrexate, azathioprine, mycophenolate mofetil, JAK inhibitors, dupilumab or other biologics).

After the treatment with any of the medications mentioned in this section, IMP may be resumed if deemed appropriate by the investigator, but not sooner than 5 half-lives after the last dose of systemic therapy.

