14.3.6 Analysis of primary efficacy endpoints

Two estimands addressing different aspects of the trial objectives will be defined:

- Primary estimand: ‘composite’.
- Secondary estimand: ‘treatment policy’.

The applied estimands incorporate 2 main types of events that influence how the treatment effects are estimated (i.e. initiation of rescue treatment and permanent discontinuation of IMP).

- **Initiation of rescue medication:** Some of the estimands use the initiation of rescue medication as an event that modifies the applied value of an endpoint, e.g. by defining a subject receiving rescue medication as a non-responder.
- **Permanent discontinuation of IMP:** This event occurs when a subject is permanently withdrawn from the treatment or the trial as described in Section 10. This can either happen at his/her own initiative or at the investigator’s discretion. The event also includes the possibility of a subject being lost to follow-up. The timing of the event is defined as the date of the early termination visit for withdrawn subjects or – in the case of a subject lost to follow-up – the date of the last known visit to the clinic. As for the rescue medication, the event type is used to modify an applied endpoint value.

All efficacy analyses will be based on the full analysis set.

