14.3.7.2 Secondary estimand for the continuous key secondary endpoints: 'hypothetical'

The secondary estimand for the continuous secondary endpoints will be:

- Treatment difference in change from baseline to Week 16 in SCORAD and DLQI, respectively, if all subjects adhered to the treatment regimen in the sense that they did not discontinue IMP permanently and no rescue medication was made available before Week 16.

The secondary estimand assesses the expected benefit when adhering to the treatment regimen tralokinumab+TCS with no rescue medication as compared to a treatment regimen with placebo+TCS with no rescue medication.

Primary analysis for the secondary estimand - continuous key secondary endpoints

Data collected after permanent discontinuation of IMP or after initiation of rescue medication will not be included in the analysis. For subjects without any post-baseline data, the baseline value will be carried forward as the first post-baseline assessment, corresponding to imputing a change of 0 at the first post-baseline assessment. This is to ensure that all subjects will be included in the analysis. The endpoints will be analysed using a repeated measurements model on the post-baseline responses up to Week 16 with an unstructured covariance matrix, Kenward-Roger approximation to estimate denominator degrees of freedom, and the mean modelled as follows (shown for change from baseline in SCORAD):

Change from baseline in SCORAD

= treatment \times visit + baseline SCORAD \times visit + baseline IGA

This model assumes that data is missing at random within each treatment arm. The estimates will be presented with 95% CI at each visit. The primary comparison between tralokinumab+TCS and placebo+TCS will be at Week 16.

Sensitivity analysis for secondary estimand - continuous key secondary endpoints

Rather than assuming that observations are missing at random within each treatment arm it is assumed that missing data from subjects who discontinue IMP/receive rescue medication in the tralokinumab+TCS arm will resemble data from subjects from the placebo+TCS arm who do not discontinue IMP/receive rescue medication.

Imputation of missing data at Week 16 will be done using a pattern mixture model where missing data in the tralokinumab+TCS arm as well as the placebo+TCS arm will be imputed from the placebo+TCS arm (using multiple imputations in a so-called copy-reference approach).

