6.8.5 Treatment and trial completers

A subject who has not permanently discontinued IMP before Week 16 will be defined as a treatment completer.

Trial completers will be defined as stated in the protocol. Reason for not completing the trial will be assessed using the alternatives listed for not attending the safety follow-up visit except for the alternatives ‘transferred to 1337’ and ‘safety follow-up information collected at nominal Week 16 visit’.

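### SAP 6.8.2 can date permanent IMP discontinuation at an AE onset that precedes doses actually given

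*SAP*

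**What the plan says.** SAP 6.8.2 defines the date for subjects with a recorded reason for permanent discontinuation. The first rule is "Defined as the latest of date of early termination visit (if existing) or date of onset of latest AE leading to withdrawal" of trial product. If neither an early termination visit nor such an AE exists, the fallback is "otherwise date of the last visit, excluding safety follow-up and nominal Week 16 visits".

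The same section derives exposure end from this date. It takes the Week 16 visit if there is one, then the date of permanent discontinuation, and only as third choice "otherwise date of last IMP administration at time 23:59:00". That third choice is the only use of the last dose in the section.

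The protocol differs. Section 10.1 treats permanent discontinuation as an active decision to stop all further dosing. Section 14.3.6 gives the timing: "The timing of the event is defined as the date of the early termination visit for withdrawn subjects", or the last known clinic visit for a subject lost to follow-up. AE onset is not mentioned. SAP 6.8.7 says that intercurrent events are handled as in the protocol.

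The date acts as a data cut. Protocol 14.3.7.2 states: "Data collected after permanent discontinuation of IMP or after initiation of rescue medication will not be included in the analysis". Section 14.3.8 carries this model over to percentage EASI change and to change in itch, sleep and POEM. Section 14.3.9 applies the same exclusion to TCS use, and 14.3.7.1 applies it to the data that fit the composite imputation model.

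**The concern.** An AE can begin well before anyone decides to stop treatment because of it. If dosing goes on in the meantime and no early termination visit takes place, the SAP rule falls back to the AE onset. The analysis then treats as post-discontinuation a stretch in which the subject was still being dosed. This conflicts with the decision-based definition in protocol 10.1 and has no counterpart in protocol 14.3.6.

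Two things are at stake:

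- **Efficacy.** Valid on-IMP visits are removed from analyses meant to estimate the effect under adherence. In a repeated-measures model the last retained visits shape the implied Week 16 value, so that subject's contribution would rest on a truncated early course.
- **Safety.** Exposure can end before dosing ends, and AEs that start during dosing can be tabulated in the wrong period.

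**Working it through.** The plan states no figure on this point, so the check applies the rule literally.

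**Rule.** SAP date = the later of the early termination (ET) visit and the onset of the latest AE leading to withdrawal. With no ET visit it is the AE onset alone.

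**Schedule.** Dosing is every 14 days from Day 0 to Week 14, Day 98 (protocol 9.2.1). The cases below are illustrative.

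| AE onset | Last dose | ET visit | SAP date | SAP date minus last dose | Doses after SAP date |
|---|---|---|---|---|---|
| Day 20 | Day 56 | none | Day 20 | 20 − 56 = −36 days | 3 (Days 28, 42, 56) |
| Day 10 | Day 56 | none | Day 10 | 10 − 56 = −46 days | 4 |
| Day 10 | Day 84 | none | Day 10 | 10 − 84 = −74 days | 6 |
| Day 28 | Day 42 | none | Day 28 | 28 − 42 = −14 days | 1 |
| Day 10 | Day 84 | Day 98 | Day 98 | 98 − 84 = +14 days | 0 |

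The fourth row could arise under the laboratory criterion in protocol 10.2.1 that requires an abnormality lasting more than 2 weeks, if dosing continues meanwhile. The last row shows that an ET visit removes the problem.

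**Data dropped in the first case.** Visits at Weeks 4, 6 and 8 (Days 28, 42, 56) lie after Day 20. Assessments scheduled at those visits are excluded from the analyses that use the cut, although a dose was given at each.

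**Exposure and AEs in the first case, with no Week 16 visit.** Exposure end is Day 20 and the last dose is Day 56, so exposure is at least 36 days short (36/365.25 ≈ 0.10 patient-years). SAP 6.7.1 and Table 4 start safety follow-up on the day after exposure end, so an AE starting between Day 21 and Day 56 is assigned to follow-up. Protocol 14.3.3, by contrast, runs exposure to the last application of IMP.

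**How many subjects.** Protocol 5.2 gives AE-related permanent discontinuation of 2.3% (tralokinumab) and 2.8% (placebo) in the earlier AD pool. With about 50 per arm:

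- tralokinumab: 50 × 0.023 = 1.15
- placebo: 50 × 0.028 = 1.40
- total: 2.55, about 2.6
- chance of at least one: 1 − 0.977^50 × 0.972^50 = 0.92

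These count all AE discontinuations. The documents give no rate for missed ET visits, so the number affected lies between zero and this figure.

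**With a lower bound.** The date becomes the later of the SAP date and the last dose. The first case moves to Day 56, no dose follows it, and the three visits are kept. The last planned dose is at Week 14, so for dosing on schedule the bound cannot move a discontinuation past Week 16.

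**The case against.** The strongest reply is that several conditions must coincide. Protocol 10.3 asks every subject who discontinues or withdraws to attend an early termination visit as soon as possible, and if that visit exists the AE onset cannot pull the date before it. Protocol Appendix 2 requires a new AE record when severity worsens, and the SAP uses the latest AE, which shortens the lag. Both points stand and limit the frequency. Neither covers an AE that persists at the same severity in a subject who skips the visit.

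Second, SAP 6.8.7 defers to the protocol, whose timing rule has no AE onset. If protocol 14.3.6 governs the efficacy cut, the error disappears there. But neither document says which date governs. Protocol 14.3.6 also gives no date for an AE discontinuation with neither an early termination visit nor loss to follow-up, which is the case the SAP fills with AE onset. The deferral does not repair exposure end or AE period assignment.

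Third, the effect on results is likely to be slight. The protocol plans no formal testing (14.3.5). As an assumed illustration, a 20-point SCORAD error in one subject's implied Week 16 value moves a 50-subject arm mean by 20/50 = 0.4 points on a 103-point scale. This stands, and it is why the severity is low.

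A reader might also infer the opposite error: the date can fall weeks after the last dose when a suspension becomes permanent, or no date exists when no reason is recorded. The documents do not support calling these errors:

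- The intercurrent event is a decision to stop, not a suspension. Protocol 10.2.2 foresees that "IMP may be resumed if deemed appropriate by the investigator", so data before the decision are kept by design.
- A cut at 14 days after the last dose would change the estimand.
- Protocol 11.8 makes the end of treatment form ask every randomised subject's site about permanent discontinuation and requires a reason if the answer is yes. The SAP 6.8.5 definition, "A subject who has not permanently discontinued IMP before Week 16 will be defined as a treatment completer", is consistent with that.
- Treating anyone with no dose through Week 14 as discontinued would catch a subject who missed only the Week 14 dose. With a 14-day limit and a 3-day visit window the cut is 84 + 14 + 3 = Day 101, which deletes the observed Week 16 value at Day 112.

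**Conclusion.** The point holds in one direction only. Read literally, SAP 6.8.2 can place permanent discontinuation before doses that were given. This requires an AE leading to withdrawal, no early termination visit, and dosing after the AE onset. The exposure and AE-period consequence further requires no Week 16 visit under the wording of 6.8.2.

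The size is small: at most about 2.6 subjects expected in 100, if the AD-pool rates carry over to this trial, and possibly none. The primary composite analysis of IGA 0/1 and EASI75 does not use the date as a cut. No effect on a treatment difference has been shown. What remains is a derivation error in a rare case, plus two timing rules that need to be reconciled. Low severity.

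**What to change.** In SAP 6.8.2, add that the date of permanent discontinuation, and any exposure end derived from it, is no earlier than the date of last IMP administration. State that this one date governs the data cut in the efficacy analyses, and reconcile it with protocol 14.3.6 and the deferral in SAP 6.8.7. Add no upper bound and no reclassification by missed doses.

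The cost is a sentence or two in the SAP and one extra term in the derivation. The date of last IMP administration is already collected on the end of treatment form (protocol 11.8). No estimand, visit or treatment rule changes.

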Panel 3: Objectives and endpoints

Objectives	Endpoints
Primary objective	
To evaluate the efficacy of tralokinumab in combination with TCS compared with placebo in combination with TCS in treating moderate-to-severe AD.	
Primary endpoints
 
 • IGA 0/1 at Week 16. • EASI75 at Week 16.
Secondary objective (efficacy)	
Key secondary endpoints
 
 • Change in SCORAD total score from baseline to Week 16. • Change in DLQI score from baseline to Week 16. • Reduction of Worst Daily Pruritus NRS score (weekly average) ≥ 4 from baseline to Week 16. 
Secondary endpoints
 
 • EASI90 at Week 16. • EASI50 at Week 16. • Percentage change in EASI score from baseline to Week 16. • Change in Worst Daily Pruritus NRS score (weekly average) from baseline to Week 16. • Change in Eczema-related Sleep NRS score (weekly average) from baseline to Week 16. • Change in POEM score from baseline to Week 16. 
Other endpoints
 
 • Reduction of DLQI score ≥ 4 points from baseline to Week 16 in subjects with baseline DLQI score ≥ 4. • Reduction of POEM score ≥ 4 points from baseline to Week 16 in subjects with baseline POEM score ≥ 4. • Amount of TCS (AxMP) used at Week 16. • TCS (AxMP) use < 5 g at Week 16. • Cumulative amount of TCS (AxMP) used from baseline to Week 16.

Objectives	Endpoints
Secondary objective (safety)	
Secondary endpoints
 
 Number of treatment-emergent AEs from baseline to Week 16 per subject. Presence of treatment-emergent ADA from baseline to Week 16.
Other objectives	
Exploratory endpoints
 
 EASI75 at each scheduled assessment. IGA 0/1 at each scheduled assessment. Change in SCORAD total score from baseline to each scheduled assessment. Change in Worst Daily Pruritus NRS score (weekly average) from baseline to each scheduled assessment. Change in DLQI score from baseline to each scheduled assessment. Reduction of Worst Daily Pruritus NRS score (weekly average) ≥ 4 from baseline to each scheduled assessment. Change in Eczema-related Sleep NRS score (weekly average) from baseline to each scheduled assessment. Change in POEM score from baseline to each scheduled assessment.

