14.3.12.1 Adverse events

AEs will be coded during the course of the trial according to Medical Dictionary for Regulatory Activities (MedDRA). AEs will be presented by PT and primary system organ class (SOC).

Treatment-emergent AEs will be summarised; however, all AEs recorded during the course of the trial will be included in subject data listings. An event will be considered treatment-emergent if started after the first use of IMP or if started before the first use of IMP and worsened in severity after first dose of IMP. The tabulations described in the following will only include the treatment-emergent events. In each of the tabulations, AEs are defined by MedDRA PTs within primary SOC.

An overall summary of the number of events and the number (percentage) of subjects with any treatment-emergent AEs, deaths, SAEs, premature discontinuations from the trial due to AEs, treatment-related AEs, and severe AEs will be presented.

The number of AEs and number of subjects with each type of AEs will be tabulated by treatment group.

The severity for each type of AE will be tabulated by treatment group.

The causal relationship to IMP for each type of AE will be tabulated by treatment group. Related AEs are defined as AEs for which the investigator has not described the causal

relationship to IMP as ‘not related’. The number of related AEs and the number of subjects with each type of related AE will be tabulated.

The causal relationship to AxMP (TCS) for each type of AE will be tabulated by treatment group. Related AEs are defined as AEs for which the investigator has not described the causal relationship to AxMP (TCS) as ‘not related’. The number of related AEs and the number of subjects with each type of related AE will be tabulated.

SAEs will be evaluated separately, and a narrative will be given.

AESIs and AEs leading to withdrawal from trial or permanent discontinuation of IMP will be tabulated and listed, no narratives will be given unless the events are considered as SAEs.

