The trial analysis sets are defined in the protocol and the following modifications to the analysis sets are introduced.

All subjects who are randomised to treatment and exposed to IMP will be included in the full analysis set (FAS) and will be analysed for efficacy up to Week 16. Exclusions from the FAS can be considered in special cases as described in the ICH E9 guideline, Section 5.2.1. If it is

Trial ID: LP0162-1343	Date: 15-Jun-2021	Version: 1.0 Page 8 of 22
-----------------------	-------------------	------------------------------

decided to exclude a randomised and exposed subject from the FAS, a justification addressing ICH E9 will be given.

As stated in the protocol, a safety analysis set will be defined as all randomised subjects who receive IMP.

In addition to the analysis sets defined in the protocol, a safety follow-up analysis set will be used as the basis for evaluation of adverse events during the safety follow-up period. It comprises all subjects for whom date of last contact is after the date of exposure end, where exposure end is defined as the Week 16 visit for subjects completing the treatment period, and otherwise the date of permanent discontinuation of IMP (tralokinumab/placebo) for subjects not completing the treatment period. See also Section [6.8.2](#) for further details.

For analysis of efficacy, subjects will be analysed ‘as randomised’.

For analysis of safety, subjects will be analysed ‘as treated’ according to the following rule: subjects who received at least one dose of tralokinumab will be analysed in the tralokinumab treatment group. Although this may dilute the AE rate in the tralokinumab treatment group slightly by including in the denominator subjects who only received one dose of active treatment, it will ensure that no significant drug reactions to tralokinumab will erroneously be assigned to placebo.

The decisions regarding inclusion/exclusion of subjects from the trial analysis sets will be documented in the analysis set definition document before breaking the randomisation code.

6 Statistical Analysis

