6.5 Rescue medication

Rescue treatment will be summarised and listed. Initiation of rescue treatment will be presented using a cumulative proportions plot over time instead of the Kaplan-Meier plot described in the protocol.

The table of rescue medication will include medications taken after the first dose and before the (nominal) Week 16 visit (or before day $7 \times 16 = 112$ after first dose, in case the (nominal) Week 16 visit did not take place).

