6.7.1 Adverse events

Adverse Events will be summarised and listed. The summaries will be split into the treatment period and the safety follow-up period. Adverse Events occurring prior to the first dose will only be listed.

Assignment of AEs to periods

An Adverse Event (AE) will be assigned to a given period (treatment period or safety follow-up) if the start date is after the start date and before the end date of that period (see Section [6.8.2, Table 4](#)).

For AEs with start day on the same day as the first dose was given, only AEs starting after the first dose was given will be considered treatment-emergent and assigned to the treatment period.

AEs starting on the day of exposure end (as defined in Section [6.8.2](#)) will be assigned to the treatment period.

Trial ID: LP0162-1343	Date: 15-Jun-2021	Version: 1.0 Page 15 of 22
-----------------------	-------------------	-------------------------------

For handling of incomplete start dates of AEs, see Section [6.8.3](#).

Sort order of AE tables

Generally, AE tables by system organ class and/or preferred term will primarily be sorted alphabetically by SOC, and the preferred terms within the SOC will be sorted by decreasing number of events found in any of the treatment groups. The treatment group itself will not be considered in the sorting.

Other adverse events of interest

A MedDRA search on all reported AEs will be made to capture AEs belonging to injection site reactions. The MedDRA search to capture this safety area of interest was performed using the following high-level terms (based on primary and secondary terms): ‘administration site reactions NEC’, ‘application and instillation site reactions’, and ‘injection site reactions’. As only primary terms are available in SDTM data, a list of preferred terms included within the high-level terms are used to account for secondary terms. The list has been reviewed prior to unblinding of the trial.

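### No AE summary in the SAP matches the secondary safety endpoint window of baseline to Week 16, because AEs starting after IMP discontinuation but before Week 16 are reported as safety follow-up

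*SAP*

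**What the plan says.** **Endpoint.** Protocol Section 6 (Panel 3) lists as a secondary safety endpoint "Number of treatment-emergent AEs from baseline to Week 16 per subject". Protocol 14.3.12.1 states: "An event will be considered treatment-emergent if started after the first use of IMP". It adds events that were present before first dose and worsened after it. Neither place ends the count when IMP is stopped.

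**Follow-up of discontinuers.** Protocol 10.1 separates stopping IMP from leaving the trial. Protocol 10.3 asks discontinuers to attend a nominal Week 16 visit, and 13.2 continues AE collection up to the safety follow-up visit.

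**SAP periods.** SAP Section 5 says that "exposure end is defined as the Week 16 visit for subjects completing the treatment period", "otherwise the date of permanent discontinuation of IMP (tralokinumab/placebo) for subjects not completing the treatment period". SAP 6.8.2 sets exposure end at the Week 16 visit if one exists, "otherwise date of permanent discontinuation of IMP (if existing) at time 23:59:00", with the last IMP administration as the final fallback. Table 4 there assigns all time after exposure end to safety follow-up.

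**SAP summaries.** SAP 6.7.1 assigns each AE to a period by its start date, using Table 4, and says: "The summaries will be split into the treatment period and the safety follow-up period". The SAP nowhere names the baseline-to-Week-16 endpoint or says which summary delivers it.

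**The concern.** The protocol fixes the endpoint window by time since baseline and arranges to collect the data that fill it. The SAP's treatment period, the only AE summary period that resembles that window, closes early for anyone who stops IMP. Its length then depends on a post-randomisation event that may differ between arms. A per-subject count taken from that period would use a shorter window for discontinuers than for completers.

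The two planned tables cannot simply be added to recover the endpoint. The follow-up table mixes discontinuers' events before Week 16 with completers' events after Week 16. It also rests on a different population, the safety follow-up analysis set, which the SAP introduces. SAP 6.4 computes patient-years, but no exposure-adjusted AE rate is specified that would offset the unequal windows.

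**Working it through.** The plan states no figure on this point, so there is none to reproduce. The check compares the rules and then sizes the effect under stated assumptions.

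**Step 1: which exposure end applies to a discontinuer?** SAP 6.8.2 read alone could let an attended nominal Week 16 visit count as the Week 16 visit. Three things point the other way:
- SAP Section 5 ties the Week 16 visit to subjects who complete treatment and gives non-completers the discontinuation date.
- SAP 6.5 names the nominal visit when it is meant to count: the rescue table covers "medications taken after the first dose and before the (nominal) Week 16 visit".
- SAP 6.8.2 itself treats nominal Week 16 visits as a separate kind when it defines the discontinuation date.

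The intended reading is therefore a cut at the discontinuation date. Under the other reading, Sections 5 and 6.8.2 conflict, and discontinuers without a nominal visit are still cut there.

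**Step 2: one subject followed through the rules.** Take a discontinuation date at Week 4 (Day 28) and an AE starting at Week 6 (Day 42).

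| Rule | Result |
|---|---|
| Protocol 14.3.12.1 | treatment-emergent (after first IMP) |
| Protocol Panel 3 | inside baseline to Week 16, so it counts |
| SAP Section 5 and 6.8.2 | after exposure end |
| SAP 6.7.1 with Table 4 | safety follow-up table; absent from the treatment-period table |

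SAP Table 5 (APERIODC) runs to last contact, but AEs are not assigned by it.

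**Step 3: which events move.** Only AEs starting after the discontinuation date and before Week 16. The discontinuation date is the later of the early termination visit and the onset of the latest AE leading to withdrawal of trial product. AEs starting on the day of exposure end stay in the treatment period. The AE that leads to discontinuation therefore stays there too.

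**Step 4: time moved per discontinuer.** Days moved = 112 − day of discontinuation.
- Week 4: 112 − 28 = 84 days (75%)
- Week 8: 112 − 56 = 56 days (50%)
- Week 12: 112 − 84 = 28 days (25%)

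**Step 5: time moved in the trial.** Share = d × (16 − w)/16, where d is the proportion discontinuing and w the mean week of discontinuation. Both are assumptions.
- d = 4%, w = 10: 0.04 × 6/16 = 1.5%
- d = 8%, w = 8: 0.08 × 8/16 = 4%
- d = 12%, w = 6: 0.12 × 10/16 = 7.5%

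A wider range, d from 5% to 15% and w from 12 to 4, gives 0.05 × 4/16 = 1.25% to 0.15 × 12/16 = 11.25%. On 100 subjects that is 20 to 180 of 1600 subject-weeks. All of these are upper bounds: a discontinuer who also withdraws from the trial has no later AEs to move. They measure observation time, not events.

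**The case against.** The strongest reply is that nothing is hidden. AEs after discontinuation are summarised in the follow-up period on a set built for that purpose, and every AE is listed. Separating on-treatment from off-treatment events is a coherent choice, and the SAP ends exposure time at the same point. The SAP also says that it supplements the protocol, so the protocol's uncut definition might be taken to stand. Finally, no formal testing is planned (Protocol 14.3.5).

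Much of this stands, and it rules out several stronger readings that a reader might infer:
- *AEs of discontinuers are lost, or all of them are affected.* They are reclassified, and only those with onset after the discontinuation date.
- *The AEs that cause discontinuation disappear.* SAP 6.8.2 and 6.7.1 keep them in the treatment period.
- *Events are removed selectively from one arm.* The documents give no overall discontinuation rate by arm. The nearest figures, AEs leading to permanent discontinuation in the pooled AD trials (Protocol 5.2), are 2.3% for tralokinumab and 2.8% for placebo. They cover AE-related stopping only, and are low and similar.
- *The period closes on the day of the last dose.* That needs a recorded discontinuation with neither an early termination visit nor an AE leading to withdrawal. Protocol 10.3 asks every discontinuer to attend an early termination visit.
- *Residual drug proves the split wrong.* The protocol equates 16 weeks with 5 half-lives, so one is 16/5 = 3.2 weeks. Drug is then also present in completers during Weeks 16 to 20, so this does not settle the matter.

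What the reply does not supply is a summary for the endpoint. An on-treatment table is a sound supplement, but the protocol did not define the endpoint that way, and the SAP's list of new analyses does not announce a change of window.

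**Conclusion.** The point holds as a mismatch between the protocol's endpoint and the SAP's reporting periods. For subjects who do not complete treatment, AEs between the discontinuation date and Week 16 meet the endpoint definition but are tabulated as follow-up, and no planned summary covers the endpoint window. That the treatment-period table would stand in for the endpoint is an inference, since the SAP does not say so, but no other AE summary comes close.

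The effect is probably small: at most about 1.5% to 7.5% of planned 16-week observation time if 4% to 12% discontinue at Weeks 6 to 10, and less if some of them also leave the trial. The efficacy analyses are untouched. It should be corrected because the endpoint is pre-specified and the data are already collected. The wording conflict between SAP Section 5 and 6.8.2 needs resolving in any case.

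**What to change.** 1. In SAP 6.7.1, define the secondary endpoint on the safety analysis set as treatment-emergent AEs from first dose to the Week 16 or nominal Week 16 visit, or to Day 112 if neither took place, regardless of IMP discontinuation. SAP 6.5 already uses this window for rescue medication.
2. Keep the treatment-period and follow-up tables, labelled as supplementary.
3. Reword exposure end in SAP 6.8.2 to agree with Section 5, stating that a nominal Week 16 visit does not set it for subjects who discontinued.

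The cost is one extra flag and one table; no new data are needed. If an on-treatment count is what the sponsor wants, the alternative is to amend the endpoint formally and say so.
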